3.2 Primary objective

The primary objective of the study is to assess the ability of an advanced ECMO capable resuscitation team to establish patients on ECPR within 30 minutes of collapse

3.3 Secondary objectives

The secondary objectives of the study are to assess the logistics of delivering a definitive clinical study of the efficacy of pre-hospital ECPR in terms of:

- the logistics of delivering the study including potential recruitment rates
- the safety of delivery of pre-hospital ECPR
- the survival and neurological outcome of patients included in the feasibility study
- the logistics of collecting data regarding resources used and the health economics

3.4 Primary Endpoint

The primary endpoint will be the number and proportion of patients with ROSC or ECMO flow (>50% target) within 30 minutes of the initiation of chest compressions.

3.5 Secondary Endpoints

The following secondary endpoint will be measured:

- number of patients not dispatched to as travel time too great/team unavailable
- the number of patients in whom it is attempted to start inserting guidewires but do not meet study inclusion criteria at 20 minute time out.
- the number of patients successfully cannulated between 31 and 45 minutes
- the number of patients successfully cannulated between 46 and 60 minutes
- proportion of patients who achieve ROSC prior to the 20 minutes timeout
- the number of patients in refractory cardiac arrest at 20 minutes in whom ROSC is achieved prior to ECMO flow
- time interval between call to the emergency services and ECPR team arrival
- proportion of potentially supportable patients in whom guidewire placement is attempted
- organ dysfunction during the first five days of hospital stay (Yes/No).
- survival to hospital discharge (Yes/No).
- neurological outcome at hospital discharge (modified Rankin scales)
- incidence of ECPR-related complications (failure to cannulate, vascular injury, site infection and distal leg ischaemia) obtained from AE/SAE data.

Details about resources used and health economic data will be collected to estimate the range of costs and affordability of any subsequent clinical trial or clinical service. These data will include:

- ECMO equipment used
- duration of ECMO support
- duration of intensive care unit stay
- maximum organ support on the Intensive Care Unit (ICU)
- duration of acute hospital stay
- Inpatient rehabilitation following acute hospital stay (yes/no) and duration.

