#### 4.6 Risks / benefits

The potential benefits relate to the restoration of blood flow to vital organs preventing or reducing neurological injury, renal failure, liver failure and cardiac failure. ECPR may also enable a patient to undergo coronary angiography and intervention whilst still in “cardiac arrest”. These may all translate to more patients surviving and survivors having better neurological outcomes.

The potential risks to participants are:

- vascular damage during cannulation. This will be mitigated by the use of ultrasound to guide the operator.
- bleeding. This is related to the administration of anticoagulants to prevent clotting in the extracorporeal circuit. Anticoagulation will be monitored closely during the study. Bleeding is common in the context of ECMO.
- local infection. This may be greater due to the procedure occurring outside the confines of a procedure room in a hospital. The risk of infection will be mitigated by using chlorhexidine skin preparation, allowing it to dry, large drapes to maximise the sterile field and prevent inadvertent contamination a single dose of prophylactic antibiotic directed against common skin commensal organisms.
- individuals, who would have previously died, surviving with neurological impairment

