## 5.4 Secondary outcomes

The following secondary endpoint will be measured:

- number of patients not dispatched to as travel time too great/team unavailable
- number of patients in whom it is attempted to start inserting guidewires but do not meet study inclusion criteria at 20 minute time out.
- the number of patients successfully cannulated between 31 and 45 minutes
- the number of patients successfully cannulated between 46 and 60 minutes
- proportion of patients who achieve ROSC prior to the 20 minutes timeout
- the number of patients in refractory cardiac arrest at 20 minutes in whom ROSC is achieved prior to ECMO flow
- time interval between call to the emergency services and ECPR team arrival
- proportion of potentially supportable patients in whom guidewire placement is attempted
- organ dysfunction during the first five days of hospital stay
- survival to hospital discharge
- neurological outcome at hospital discharge (Cerebral Performance Category and modified Rankin scales)
- incidence of ECPR-related complications (failure to cannulate, vascular injury, site infection and distal leg ischaemia)

Details about resources used and health economic data will be collected to estimate the range of costs and affordability of any subsequent clinical trial or clinical service. These data will include:

- ECMO equipment used
- duration of ECMO support
- duration of intensive care unit stay
- maximum organ support on the Intensive Care Unit (ICU)
- duration of acute hospital stay
- duration of inpatient rehabilitation following acute hospital stay

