Adverse climate Wind, cold, and rain may make the cannulation difficult.	2	3	6	Use of IPX4 standard equipment if possible to counter effects of rain. Covers utilised for other equipment. Weights for drapes to counter wind Suspension of service if conditions considered too adverse to safely deliver pre-hospital ECMO	2	2	4

Adverse publicity for Trust/Organisations involved An adverse outcome for the patient (severe neurological injury but survival; or death despite significant and prolonged intervention) may be perceived in retrospect as an inappropriate use of healthcare resource (e.g. ICU capacity, blood products).	2	3	6	Discussion with Communications team prior to the event – avoid all public comments until patient outcome known and consent of patient gained. Aim to undertake resuscitation out of public view	2	2	4
Reduced capacity to support other patients Any patient will take up ICU capacity in terms of bed spaces, staffing, and equipment. This may limit the ability to support the work of elective cardiac surgery or emergency respiratory ECMO.	2	3	6	Pre-hospital ECMO team are additional to the standard ECMO team which would not be influenced by the activity. Planning with the theatre schedulers and cardiac surgeons regarding.	2	2	4
Failure to cannulate femoral vessels Expected failure rate of 5-10% of percutaneous cannulation of femoral vessels in cardiac arrest. Failure would negate ability to initiate ECPR.	3	4	12	Experienced consultants, cannulating with the use of ultrasound, Saline fluid infusion to improve vessel size. Augmented reality ultrasound glasses to improve technique. Any failure to cannulate would mean patient would receive standard ongoing care as per LAS resuscitation protocols.	2	4	8
Leg ischaemia – arterial The size of the arterial cannula can impair blood flow to the ipsilateral limb. A distal limb perfusion cannula will be difficult to insert in the pre-hospital environment	3	4	12	Routine insertion of a distal limb perfusing catheter on return to the Barts Health. Use of smaller arterial cannulae (15Fr).	3	2	6

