### 15.4 Non-investigational medicinal products (NIMPs)

The non-investigation medicinal products used in the study are outlined in Table 7. Many other drugs may be used in the care of the patient as dictated by the attending clinicians.

**Table 7** Non-investigational medicinal products

Medicinal product	Comments	Storage requirements
Oxygen/Medical air mixture	Sweep gas for ECMO circuit	Keep away from extremes of heat
Rocuronium bromide	As neuromuscular blockade	2-8°C
Teicoplanin	As antibiotic prophylaxis for surgical site infection	None
Heparin sodium	As an anticoagulant for ECMO	Below 25°C
Compound sodium lactate	For priming of the ECMO circuit	None

The pre-mixed oxygen/medical air mixture will be prepared as a special gas by the British Oxygen Company. It will be stored in accordance with the Health Technical Memorandum 02-01: Medical gas pipeline systems (Part B Operational management) produced by the Department of Health and outlined in the trial Standard Operating Procedure for the Management of medical gases. Specifically, a suitable storage area (BNB\_06\_071 in King George V Building, St Bartholomew's Hospital) has been approved by the trial pharmacist. A chain of custody will be maintained for all non-investigation medicinal products. A Summary of Product Characteristics (SPC) for each NIMP will be stored in the Trial Master File. The Undesired Effects outlined in these SPC will act as Reference Safety Information to enable attribution of causality and expectedness when classifying adverse events (Section 16.3).

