Expected	
Expected events are:
 
 
-Failure to cannulate a patient for ECMO
 
-Hypoxic brain injury
 
-Death due to myocardial failure
 
-Death due to hypoxic brain injury
 
-Vascular damage during cannulation in adverse environment
 
-Bleeding at site of cannulation
 
-Infection at site of cannulation
 
-Intracranial haemorrhage
 
-Gastrointestinal haemorrhage
 
-Events outlined in the Undesired Effects section of the SPC for each NIMP
 

----------	--

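### The ECPR-related complications endpoint omits bleeding, so the only event-specific complication incidence planned excludes a harm that the protocol itself calls common on ECMO

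*SAP*

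**What the plan says.** SAP 3.5 sets as a secondary endpoint the "incidence of ECPR-related complications (failure to cannulate, vascular injury, site infection and distal leg ischaemia) obtained from AE/SAE data". Protocol 5.4 has the same definition: "incidence of ECPR-related complications (failure to cannulate, vascular injury, site infection and distal leg ischaemia". Neither list carries wording such as 'for example' or 'including', so both read as closed. SAP Table 3 assigns the endpoint to the cannulated patients (N=6), and SAP 8.1.2 reports categorical endpoints as numbers and proportions.

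On bleeding, Protocol 4.6 names four potential risks to participants. One is "bleeding. This is related to the administration of anticoagulants to prevent clotting in the extracorporeal circuit", and the same bullet adds "Bleeding is common in the context of ECMO". Heparin appears among the non-investigational products in Protocol Table 7, described as "As an anticoagulant for ECMO". Protocol Table 9, the list of expected events, includes "Bleeding at site of cannulation" and "Intracranial haemorrhage" as well as gastrointestinal haemorrhage, and has a separate entry for vascular damage.

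SAP 9 plans the number of subjects with at least one AE, the number by intensity, the total number of AEs, and a listing of SAEs showing expectedness and relatedness. It plans no table by event type.

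**The concern.** Safety of delivering the intervention is a secondary objective in both documents, and the results are meant to inform the design of a larger randomised study. The complications endpoint is the only planned summary that gives an incidence for named complications. Someone designing that next study will read it as the complication rate of pre-hospital ECPR, but it leaves out the one risk that Protocol 4.6 describes as common. Followed as written, a patient with an intracranial haemorrhage and none of the four listed events adds nothing to it.

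**Working it through.** No power, error rate or published figure attaches to this endpoint, so there is no number to reproduce. The check sets the relevant passages side by side.

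| Event | Protocol 4.6 risk | Protocol Table 5 row | Protocol Table 9 expected | Endpoint (5.4, SAP 3.5) |
|---|---|---|---|---|
| Vascular injury | yes | yes | yes | yes |
| Site infection | yes | yes | yes | yes |
| Failure to cannulate | no | yes | yes | yes |
| Distal leg ischaemia | no | yes | **no** | yes |
| Cannulation-site bleeding | yes (as bleeding) | only within vascular damage | yes | **no** |
| Intracranial haemorrhage | yes (as bleeding) | no | yes | **no** |
| Gastrointestinal haemorrhage | yes (as bleeding) | no | yes | **no** |

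1. **Could an existing item absorb bleeding?** Only in part. Table 5 associates vessel damage with extensive bleeding, so some access-site bleeds might be coded as vascular injury. Table 9, however, treats vascular damage and site bleeding as two entries. Intracranial and gastrointestinal haemorrhage fit none of the four items.

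2. **Where would a bleed be reported?** Protocol 16.1 and 16.4 require every untoward occurrence to be recorded. A serious bleed would appear in the SAE listing of SAP 9. A non-serious bleed would add to the subject and event totals and to an intensity category, none of which identifies it as a bleed.

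3. **How large is the effect?** With N = 6, each patient who bled and had none of the four events would move the proportion with any complication by 1/6 = 16.7 percentage points. The number of such patients is unknown, because the documents give no bleeding rate and some bleeding patients may already count through another item.

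4. **Is a bleed in six patients likely at all?** For illustration only, with an assumed per-patient risk p and independent patients, P(at least one) = 1 − (1 − p)^6:
   - p = 0.05: 1 − 0.95^6 = 0.27
   - p = 0.10: 1 − 0.90^6 = 0.47
   - p = 0.30: 1 − 0.70^6 = 0.88
   - p = 0.50: 1 − 0.50^6 = 0.98

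   These are chances that a bleed occurs. They do not estimate the understatement.

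5. **The leg-ischaemia row.** Table 5 anticipates this event ("The size of the arterial cannula can impair blood flow to the ipsilateral limb") and gives it an initial likelihood of 4, reassessed as 2 after mitigation. Table 9 does not list it. Protocol 16.5 ties unexpectedness to absence from Table 9, whereas Table 9 itself describes unexpected events as ones not anticipated. A serious, related case is therefore unexpected on the 16.5 rule, although Table 5 foresees it.

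**The case against.** The best defence is that the list was chosen deliberately. Its four items match the procedural rows of Table 5 (vessel damage, local infection, failed cannulation, leg ischaemia), the objective concerns delivery of ECPR, and anticoagulant-related bleeding can reasonably be left to AE/SAE reporting. This explains the list but does not rescue it. Cannulation-site bleeding is itself procedural and has its own entry in Table 9, and the endpoint is labelled as ECPR-related, not as access-related.

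Three further objections stand and limit the point.

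- A reader might infer that bleeding would go unreported, or that this endpoint is the only safety rate planned. Neither is so. SAP 9 also counts subjects with any AE, by intensity, and lists each SAE. In six patients, a listing shows every serious bleed.
- A reader might put a figure on the understatement, for instance 17 to 50 percentage points from one to three bleeding patients in six. Those counts would be assumed, and the calculation would also require that no bleeding patient had any of the four listed events.
- Neither document says that the four items will be collapsed into a single yes/no score. If they are reported one by one, the defect is a missing set of rows and not a wrong composite.

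It may also be said that counting any bleed on an anticoagulated circuit would capture trivial oozing. That is fair, and is why the fix separates serious from non-serious bleeds.

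**Conclusion.** The point holds as a gap in the endpoint definition, common to both documents; it is not a discrepancy between them. The event-specific complication incidence excludes a harm that the protocol attributes to the circuit anticoagulation and calls common. For serious bleeds the loss is one of summary, since the listing retains them. For non-serious bleeds, the planned output would not identify them as bleeds at all. The size cannot be stated from the documents. The conclusion assumes that the bracketed list is closed, as worded, and that a bleed not coded as vascular injury falls outside it. Sample size and error rates are unaffected, since the study is descriptive.

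On leg ischaemia, the mismatch between Table 5, the endpoint and Table 9 is real. A reader might conclude that it should simply be added to Table 9. The documents do not make that a neutral edit: under Protocol 16.5, listing it as expected would take serious, related cases out of the 24-hour report to the sponsor and the 15-day report to the ethics committee.

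**What to change.** In Protocol 5.4 and SAP 3.5, add cannulation-site bleeding, intracranial haemorrhage and gastrointestinal haemorrhage to the complication list, using the Table 9 terms. In the SAP, report each component separately as n/N, with bleeds split into serious and non-serious as already recorded, and add n/N with any complication. State whether a site bleed caused by vessel damage counts under one heading or both, so that the components can be read without double counting.

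The endpoint already draws on AE/SAE data, so no new data collection is needed. The costs are a wording amendment to both documents, with whatever approval Protocol 11.5 requires if it is substantial, and a complication rate that will look less favourable.

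Separately, the sponsor should reconcile Protocol 5.4, Table 5, Table 9 and 16.5 on distal leg ischaemia, weighing the effect on expedited reporting before any change to Table 9.

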3.6 Assessment of objectives

The time of ROSC or ECMO blood flow >50% target will be recorded on the CRF. Many assessments will be made as part of routine clinical practice and those below will be recorded on the CRF (Table 1). In addition, other a variety of physiological, biomarkers, and functional outcome measures, that are not part of routine clinical practice, will be recorded as secondary outcomes for the study (Table 2)

Table 1 Standard clinical assessments made that will be included in CRF (if undertaken by clinical team)

Assessment	4 h	24 h	Any time point in 7 d
RIFLE score ^a		✓	
Computed tomography of brain			✓
Electroencephalography			✓
Somatosensory evoked potentials			✓
Liver function tests ^b	✓	✓	✓
Echocardiography ^c			✓
Vital signs ^d	✓	✓	
Vasoactive medication use ^e	✓	✓	
Coagulation assessments ^f	✓	✓	

^a The RIFLE score is a classification of acute kidney injury based on creatinine levels and urine output

^b Specifically bilirubin, aspartate transaminase, alkaline phosphatase

^c A comprehensive study as outlined by the British Society of Echocardiography

^d Including heart rate, blood pressure, right atrial pressure, pulmonary artery occlusion pressure, cardiac output and lactate

^e Including adrenaline, noradrenaline, dobutamine, dopamine, milrinone, levosimendan

^f Including prothrombin time, activated partial thromboplastin time, fibrinogen, platelet count

Table 2 Non-routine assessments made during the study

Assessment	Pre-ECMO	Time of hospital admission				Hospital discharge	3 month
		0 h	24 h	48 h	72 h		
Bilateral pupillometry	✓	✓	✓	✓	✓		
Serum Neuron Specific Enolase		✓	✓	✓	✓		
Plasma/Serum biobanked ^a	✓	✓	✓	✓	✓		
Modified Rankin Scale						✓	✓
Function Independence Measure						✓	✓
EQ-5D							✓

^a Biomarkers measured will be Troponin I, BNP, CKMB, NSE and SB100.

3.6.1 Assessment of primary endpoint

The time to cannulation will be calculated as the time from collapse to the ECMO start time and from this the number of patients cannulated within 30 minutes will be obtained.

3.6.2 Assessment of secondary endpoints

Secondary endpoints are described in section 7.5.

Clinical assessment data to be collected is described in section 7.6 along with details of the time points for each endpoint.

Use of the EQ-5D-5L, modified Rankin scale and Functional Independence Measure will be outlined in a trial Standard Operating Procedure.

FIM will be assessed over the domains of self-care, sphincter control, transfers, locomotion, communication and social cognition, as well as motor and cognitive subtotal scores and total FIM score [4]. EQ-5D-5L will be described for 5 dimensions, as well as the visual analogue scale. In addition, a single index value will be calculated (www.euroqol.org).

3.7 Level of significance

The study is descriptive and no hypothesis tests will be conducted.

3.8 Sample size

No power calculation has been undertaken. The study aims to recruit six patients. The sample size has been selected to allow robust data to support a future efficacy study.

4 General Analysis Definitions

4.1 Study period and visit definitions

4.1.1 Visits

On arrival at the scene the ECPR team will assess inclusion/exclusion criteria. If the appropriate criteria are met:

The pre-hospital ECPR team will support the LAS in endeavouring to achieve ROSC.

The ECMO consultants will insert guidewires into femoral vessels and prepare CardioHelp.

If ROSC is achieved within 20 minutes of starting resuscitation, the team will support LAS with standard post-resuscitation care and transfer of the patient to the nearest Heart Attack Centre.

If ROSC is not achieved within 20 minutes the exclusion criteria will be reassessed and if no exclusion criteria are identified the ECMO consultants will proceed to cannulate the patient's femoral artery and vein and commence ECMO support. If cannulation cannot be achieved within 60 minutes then further attempts will not be continued and the patient will be reviewed with consideration to declaring life extinct or transporting the patient under ongoing CPR to the nearest emergency department.

FIM and modified Rankin scale will be assessed at hospital discharge and at 3 months, and EQ-5D-5L at 3 months.

The end of the study is defined as 90 days after the final patient is recruited into the study.

4.1.2 Study Scheme Diagram

A flow diagram of study procedures is given in the protocol (section 8.10).

4.1.4 Subgroup definitions

Not applicable.

5 Patient Disposition

Participants will be patients with a visible age between 18 and 65 who have a witnessed out-of-hospital cardiac arrest with presumed cardiac aetiology, receive bystander chest compressions within 3 minutes and remain in cardiac arrest or fail to sustain ROSC at 20 minutes. Exclusion criteria are detailed in the protocol section 6.2. Numbers enrolled, withdrawing and completing discharge and 3 month follow-up will be reported.

5.1 Compliance to study drug

Not applicable.

5.2 Exposure to study drug

Not applicable.

6 Demographics and Baseline characteristics

Age, gender, ethnicity and time of LAS attendance on scene will be described for intervention patients and matched controls. In addition, we will describe the following risk factors – diabetes, PVD, IHD, CVA, smoking, frailty index.

7 Interim analysis and timing for analysis.

7.1 Interim analysis

No formal interim analysis is planned. A Data Safety Monitoring Committee (DSMC) will be set up and will be responsible for monitoring trial data and making recommendations on whether it is ethical and safe to continue the study. Recruitment, safety and demographic

information of participants will be reported to the DSMC. Additional analysis may be undertaken if requested by the DSMC.

7.2 Time points for analysis.

The DSMC will meet at least every three months. All other analysis will take place at the end of the study.

8 Efficacy Analysis

8.1 Method for analysis of endpoints

8.1.1 Analysis of primary endpoint

Analysis will be descriptive. Results will be presented as the total number, and the number and proportion of patients with ROSC or ECMO flow (>50% target) in the treated population.

